4.3.2 OPEN/IWRS User Requirements

OPEN/IWRS users must meet the following requirements:

- Have a valid CTEP-IAM account (*i.e.*, CTEP username and password).
- To enroll patients or request slot reservations: Be on an ETCTN Corresponding or Participating Organization roster with the role of Registrar. Registrars must hold a minimum of an AP registration type.
- To approve slot reservations or access cohort management: Be identified to Theradex as the "Client Admin" for the study.
- Have regulatory approval for the conduct of the study at their site.

Prior to accessing OPEN/IWRS, site staff should verify the following:

- All eligibility criteria have been met within the protocol stated timeframes.
- If applicable, all patients have signed an appropriate consent form and Health Insurance Portability and Accountability Act (HIPAA) authorization form.

4.3.3 Special Instructions for Patient Enrollment

This Study will use the ETCTN Specimen Tracking System (STS).

- All biospecimens collected for this trial must be submitted using the ETCTN Specimen Tracking System (STS) unless otherwise noted.
- The system is accessed through special Rave user roles: "CRA Specimen Tracking" for data entry at the treating institutions and "Biorepository" for users receiving the specimens for processing and storage at reference labs and the Biorepository.
- Please refer to the Medidata Account Activation and Study Invitation Acceptance link on the CTSU website under the Rave/DQP tab.

• Important: Failure to complete required fields in STS may result in a delay in sample processing. Any case reimbursements associated with sample submissions will not be credited if samples requiring STS submission are not logged into STS.

Detailed instructions can be found in Section 5.3.

4.4 General Guidelines

Following registration, patients should begin protocol treatment within 5 business days. Issues that would cause treatment delays should be discussed with the Principal Investigator. If a patient does not receive protocol therapy following registration, the patient's registration on the study may be canceled. The Study Coordinator should be notified of cancellations as soon as possible.

5. BIOMARKER, CORRELATIVE, AND SPECIAL STUDIES

5.1 Summary Table for Specimen Collection

Time Point	Specimen	Send Specimens To:			
PRE-TREATMENT (after informed consent and within 14 days of Cycle 1 Day 1)					
	• 4-8 formalin fixed cores ¹	ETCTN Biorepository			
	• 10 mL blood in EDTA tube				
ON-TREATMENT	(C2 D3-5, 2-6 hours post AM olaparib and tem	ozolomide treatment)			
	• 4-6 formalin fixed cores ¹	ETCTN Biorepository			
PRE-PROGRESSION (if applicable, see Section 5.4.2)					
	• 4-8 formalin fixed cores ¹	ETCTN Biorepository			
¹ For new biopsies, a copy of the radiology and operative reports from the tissue removal procedure must					
be sent with the tissue	be sent with the tissue to the ETCTN Biorepository. When completed, upload the corresponding				

pathology reports to Rave.

5.2 Specimen Procurement Kits and Scheduling

5.2.1 Specimen Shipping Kits

Kits for the collection and shipment of specimens to the ETCTN Biorepository can be ordered online via the Kit Management system: (https://ricapps.nationwidechildrens.org/KitManagement).

Users at the clinical sites will need to set up an account in the Kit Management system and select a specific clinical trial protocol to request a kit. Please note that protocol may include more than one type of kit. Each user may order two kit types per protocol per day (daily max = 6 kits). Kits are shipped ground, so please allow 5-7 days for receipt. A complete list of kit contents for each kit type is located on the Kit Management system website.

Note: Kits or supplies are only provided for specimens shipped to the Biorepository. Institutional supplies must be used for all other specimen collection and processing.

5.2.2 Scheduling of Specimen Collections

Please adhere to the following guidelines when scheduling procedures to collect tissue:

- Tumor tissue specimens collected during biopsy procedures and fixed in formalin must be shipped on the same day of collection.
- Tissue can be collected Monday through Wednesday and shipped overnight for arrival on Tuesday through Thursday at the ETCTN Biorepository at Nationwide Children's Hospital.
- Fresh blood specimens may be collected and shipped Monday through Friday.

5.3 Specimen Tracking System Instructions

5.3.1 Specimen Tracking System Overview and Enrollment Instructions

For the ETCTN STS, the following information will be requested:

- Protocol Number
- Investigator Identification
 - Institution and affiliate name
 - Investigator's name
- Eligibility Verification: Patients must meet all the eligibility requirements listed in Section 3.
- Additional Requirements:
 - Patients must provide a signed and dated, written informed consent form.

Upon enrolling a patient, IWRS will communicate with OPEN, assigning two separate and unique identification numbers to the patient, a Universal patient ID (UPID) and a Treatment patient ID. The UPID is associated with the patient and used each and every time the patient engages with the portion of this protocol that uses the ETCTN Specimen Tracking System. The UPID contains no information or link to the treatment protocol. IWRS will maintain an association between the UPID for ETCTN biobanking and molecular characterization and any treatment protocols the patient participates in, thereby allowing analysis of the molecular characterization results with the clinical data.

NCI Protocol #: 10250 Version Date: February 14, 2023

Immediately following enrollment, the institutional anatomical pathology report for the diagnosis under which the patient is being enrolled must be uploaded into Rave. The report must include the surgical pathology ID (SPID), collection date, block number, and the IWRS-assigned UPID and patient study ID for this trial. For newly acquired biopsies, the radiology and operative report(s) must also be uploaded into Rave. **Important: Remove any personally identifying information, including, but not limited to, the patient's name, initials, medical record number, and patient contact information from the institutional pathology report prior to submission.**

Additionally, please note that the STS software creates pop-up windows when reports are generated, so you will need to enable pop-ups within your web browser while using the software.

For questions regarding the Specimen Tracking System, please contact the Theradex Help Desk at [contact].

A shipping manifest **must** be included with all sample submissions.

5.3.2 Specimen Labeling

5.3.2.1 Tissue Specimen Labels

Include the following on all tissue specimens or containers (*e.g.*, formalin jar):

- Patient Study ID
- Universal Patient ID (UPID)
- Specimen ID (automatically generated by Rave)
- Time point
- Specimen type (FFPE Block, Formalin Fixed Tissue, Fresh Tissue in Media, etc.)
- Tissue type (P for primary, M for metastatic or N for normal)
- Surgical pathology ID (SPID) number
- Block number from the corresponding pathology report (archival only)
- Collection date (to be added by hand)

[figure not shown]
5.3.2.2 Blood Specimen Labels

Include the following on blood specimens (including whole blood and frozen, processed blood products – like serum and plasma):

- Patient Study ID
- Universal Patient ID (UPID)
- Specimen ID (automatically generated by Rave)
- Time point
- Specimen type (*e.g.*, blood, serum)
- Collection date (to be added by hand)

5.3.2.3 Example of Specimen Label

The following image is an example of a tissue specimen label printed on a standard Avery label that is 1" high and 2.625" wide.

The QR code in the above example is for the Specimen ID shown on the second line. **NOTE:** The QR code label is currently under development at Theradex as of 31-Aug-2018; therefore, labels generated by the STS for this study may not include a QR code.

The second line item from the end includes four data points joined together:

- 1. Tissue only: Primary (P), Metastatic (M), Normal (N) tissue indicated at the beginning of the specimen ID; this field is blank if not relevant (e.g., for blood)
- 2. Block ID or blank if not relevant
- 3. SPID (Surgical Pathology ID) or blank if none
- 4. The last alpha-numeric code is protocol specific and is only included if the protocol requires an additional special code classification

The last line on the example label is for the handwritten date and optional time.

5.3.3 Overview of Process at Treating Site

5.3.3.1 OPEN Registration

All registrations will be performed using the Oncology Patient Enrollment Network (OPEN) system. OPEN communicates automatically with the Interactive Web Response System (IWRS) which handles identifier assignments, any study randomization and any prescribed slot assignments. If specimen analysis is required to determine eligibility, the protocol will be setup with multi-step registration.

Registration without eligibility specimen analysis:

- 1. Site enters registration data into OPEN during one or more steps.
- 2. IWRS receives data from OPEN, generates the Patient Study ID and the Universal Patient ID, both of which are sent back to OPEN.
- 3. IWRS sends all applicable registration data directly to Rave at the end of the final registration step.

Any data entry errors made during enrollment should be corrected in Rave.

5.3.3.2 Rave Specimen Tracking Process Steps

Step 1: Complete the **Histology and Disease** form (but do not upload reports until a specimen label can be applied to them) and the Baseline forms regarding **Prior Therapies**. Enter the initial clinical specimen data:

• **Specimen Tracking Enrollment** CRF: Enter Time Point, Specimen Category, Specimen Type, Block number, Tissue type, Surgical Path ID, and number of labels needed (include extra labels to apply to reports to be uploaded). CRF generates unique Specimen ID.

Step 2: Print labels using report in EDC and collect specimen.

- Label specimen containers and write collection date on each label.
- After collection, store labeled specimens as described in Section 5.3
- Apply an extra specimen label to each report before scanning. Return to the **Histology and Disease** form to upload any initial Pathology, Radiology, Molecular Reports (up to 4), Surgical (or Operative) reports and Pathology Verification form (when applicable). Return to **Specimen Tracking Enrollment** CRF to upload any molecular report (one per specimen) and/or specimen specific pathology or related report (one per specimen). Uploaded reports should have protected health information (PHI) data like name, mailing address, medical record number or social security number (SSN) redacted. Do not redact surgical pathology ID (SPID), block number or relevant dates, and include UPID and patient study ID on each document.

Step 3: Complete specimen data entry.

• **Specimen Transmittal** Form: Enter Collection date and time and other required specimen details.

Step 4: When ready to ship, enter shipment information.

- Shipping Status CRF: Enter tracking number, your contact information, recipient, number of containers and ship date once for the 1st specimen in a shipment.
- **Copy Shipping** CRF: Select additional specimens to add to an existing shipment referenced by the tracking number.

Step 5: Print shipping list report and prepare to ship.

- Print two copies of the shipping list, one to provide in the box, the other for your own records.
- Print pathology or other required reports to include in the box. Be sure the printed copy includes the specimen label.

Step 6: Send email notification.

• For only one of the specimens in the shipment, click "Send Email Alert"

NCI Protocol #: 10250 Version Date: February 14, 2023

checkbox on the Shipping Status CRF to email recipient.

Step 7: Ship the specimen(s).

5.4 Specimen Collection and Processing

5.4.1 Biopsy Collection Procedure

Mandatory core biopsy specimens will be obtained at two time points. The first ("pretreatment") biopsy will be obtained before beginning study treatment (after informed consent is obtained and up to 14 day prior to cycle 1 day 1). The second ("on-treatment") biopsy will be performed during cycle 2, days 3-5.

A third, optional ("pre-progression") biopsy will be collected from patients who meet certain criteria and provide informed consent for this biopsy (see Section 5.4.2 below).

5.4.2 Optional "Pre-Progression" Tumor Biopsy

The investigators will seek to evaluate the RAD51, MGMT, and SLFN11 assays in patients who have evidence of clinical benefit from the study drug but later show evidence of radiographic progression not meeting RECIST criteria for progressive disease.

To undergo this biopsy, all of the following criteria must be met:

- 1. The patient has provided informed consent for the optional tumor biopsy, which is part of the informed consent document for this study.
- 2. The patient has evidence of clinical benefit from study treatment manifest by either:
 - a. RECIST complete or partial response within the first 6 months of study treatment
 - b. Stable disease, by RECIST criteria, of at least 4 cycles (12 weeks) duration
- 3. At a subsequent timepoint, the patient has study-specified imaging showing evidence of radiographic disease progression, but which does not meet RECIST criteria for progressive disease (RECIST + 5-19% from the baseline study) and the patient lacks clinical progression, and the investigator intends to continue the study treatment.

When all of these criteria apply, a third ("pre-progression") tumor biopsy will be performed. The same procedures as described in Section 5.4.1 will apply to this biopsy. The biopsy will occur during days 3-5 of the next treatment cycle initiated following the timepoint at which these criteria are met, 2-6 hours post AM olaparib and temozolomide treatment. The same site of disease should be biopsied if at all possible.

If questions arise regarding whether a given patient is considered appropriate for the optional biopsy, the treating investigator should discuss with the principal investigator prior to the procedure.

5.4.3 Formalin-Fixed Tumor Biopsies

- 1. Label formalin-filled containers according to instructions in section 5.3.1.1.
- 2. Obtain the designated number of core biopsies (see Section 5.1) using a 16-gauge or 18-gauge core needle, and place one core in each cassette.
- 3. Snap the cassette lids closed and place cassettes into a formalin-filled pre-labeled container as soon as possible after collection to prevent air drying. Up to two cassettes may be placed in one formalin jar.
- 4. Secure the container lids and place the containers into the shipping kit according to instructions in section 5.5. Keep tissue in formalin jars at room temperature until shipment to the ETCTN Biorepository.

5.4.4 Blood Collection for Germline Testing

During the screening period, a blood sample will be collected to serve as a germline sample for evaluation during the whole exome sequencing/RNAseq analysis.

5.4.4.1 Collection of Blood in EDTA Tubes

- 1. Label EDTA tubes according to the instructions in section 5.3.1.2.
- 2. Collect 10 mL blood in EDTA tube(s) and gently invert tube to mix.
- 3. Ship on day of collection (whenever possible) according to instructions below.
- 4. If blood cannot be shipped on the day of collection (*e.g.*, a late scheduled collection), then refrigerate until shipment.

5.5 Shipping Specimens from Clinical Site to the ETCTN Biorepository

Core biopsies that are fixed in formalin and fresh blood should be shipped as one shipment at ambient temperature, whenever possible. The same box sent with kit contents should be used to ship specimens to the ETCTN Biorepository. In winter months, please include extra insulation, such as bubble wrap, inside the shipping container.

For formalin-fixed biopsies, if the corresponding anatomical pathology report is not available at the time of shipment, then the surgical and/or radiology report must be uploaded to the ETCTN specimen tracking system and included in the package, or the specimen will not be processed.

5.5.1 Specimen Shipping Instructions

Tissue in formalin must be shipped on the day of collection. Collect and ship on Monday through Wednesday.

Fresh blood may be shipped on Monday through Friday. Please select "Saturday Delivery" when shipping fresh blood on a Friday.

5.5.1.1 Shipping Ambient Tissue and Blood in a Single-Chamber Kit

- 1. Before packaging specimens, verify that each specimen is labeled according to the instructions above and that the lids of all primary receptacles containing liquid are tightly sealed. Formalin jars should be wrapped in parafilm.
- 2. Place the specimens in zip-lock bags. Use a separate bag for each specimen type.
- 3. Place specimens into a biohazard envelope with absorbent material. Expel as much air as possible and seal the envelope securely.
- 4. Place the biohazard envelope into a Tyvek envelope. Expel as much air as possible and seal securely.
- 5. Place the specimen(s) and a copy of the shipping manifest and corresponding reports such as surgical or radiology reports into the insulated shipping container. In winter months, please include extra insulation, such as bubble wrap, inside the shipping container, to prevent specimens from freezing.
- 6. Place the lid on top of the container. Close the outer flaps and tape shut.
- 7. Attach a shipping label to the top of the shipping container.
- 8. Attach an Exempt Human Specimen sticker to the side of the container.
- 9. Ship specimens via overnight courier to the address below. FedEx Priority Overnight is strongly recommended to prevent delays in package receipt.

5.6 Biomarker Plan

Priority	Biomarker Name	Biomarker Assay	Biomarker Type and Purpose	M/O	Timing	Specimen and Quantity Needed	Laboratory
1	Genomic alterations in HR pathway genes	Whole exome sequencing and RNAseq	Integrated To assess for genomic alterations in genes relevant to homologous recombination repair and assess effect of such alterations on clinical response to treatment.	M	Pre-treatment Pre-treatment	DNA and RNA from Tumor biopsy 2 cores DNA from Whole Blood (for germline) 10 mL	Molecular Characterization and Clinical Assay Development Laboratory (MoCha) Frederick National Laboratory for Cancer Research (NCI) [name]
2	Functional HR assay (RAD51)	RAD51 foci, H2AX and geminin by IHC	Integrated To evaluate whether RAD51 foci formation as assessed at baseline or while on-treatment is correlated with response to treatment. To evaluate whether patients who show initial clinical benefit but develop radiographic progressive disease have a change in assay result using an optional biopsy.	M M O	Pre-treatment On-treatment (C2D3-5) Pre-progression	10 unstained slides from tumor biopsy per timepoint	Brigham and Women's Hospital Pathology Core [name], Dana Farber Cancer Institute
3	SLFN11 expression	SLFN11 expression by IHC and possible mRNA	Exploratory To evaluate whether SLFN11 expression is predictive of clinical response to treatment.	0	Pre-treatment Pre-progression	10 unstained slides from tumor biopsy per timepoint	Developmental Therapeutics NCI [name], PhD
4	MGMT expression	MGMT expression by IHC and possible mRNA	Exploratory To evaluate whether MGMT expression is predictive of clinical response to treatment.	0 0	Pre-treatment Pre-progression	10 unstained slides from tumor biopsy per timepoint	Developmental Therapeutics NCI [name], PhD

List of Biomarker Assays in Order of Priority

NCI Protocol #: 10250 Version Date: February 14, 2023

IHC=Immunohistochemistry, NGS=Next generation sequencing, MGMT=O[6]-methylguanine-DNA methyltransferase, SLFN11=Schlafen family member number 11, RAD51= DNA repair protein RAD51 homolog; mRNA = messenger RNA.

5.7 Integrated Correlative Studies

Specimens from this study will be received, accessioned, paraffin embedded and stored per ETCTN Biorepository guidelines. Once the study is completed and all material has been received, nucleic acids/DNA will be isolated per established procedures and sent to the NCLN Genomics laboratory for further analysis. Slides will be made and distributed in batch to the laboratory performing the RAD51 correlative study. The prioritization of tissue for the study is shown in Section 5.6.

5.7.1 Genomic Alterations in HR Pathway Genes

5.7.1.1 Specimen Receipt and Processing at the ETCTN Biorepository

Formalin-fixed tissue from the pre-treatment time point will be used for this assay. Tissue in formalin will be processed and embedded upon receipt at the ETCTN Biorepository, and slides will be cut from the biopsies. For all tumor specimens, the first section will be stained with hematoxylin and eosin (H&E) for pathology quality control review to assess tumor content; unstained slides will be macrodissected, if needed, and scraped for DNA and RNA co-extraction. DNA will be banked in a stock vial and RNA will be divided into 5 aliquots; all nucleic acids will be stored in a -80°C freezer until distribution for testing.

DNA will be extracted from blood collected in an EDTA tube at the pre-treatment time point. DNA will be stored in a -80°C freezer until distribution for testing.

5.7.1.2 Site Performing Correlative Study

Whole exome sequencing (WES) and RNAseq will be conducted in pre-treatment biopsies at the Molecular Characterization and Clinical Development Laboratory (MoCha) of the NCI. The assay will specifically evaluate for genomic mutations, copy number changes and loss of heterozygosity in pre-specified HR pathway genes (BRCA1, BRCA2, ATM, ATR, ATRX, CHK1, CHK2, RAD51, PALB2, FANCA, and NBS1) using the MoCha pipeline. Alterations in other genes will analyzed by the MoCha WES/RNAseq pipeline will also be characterized and reported.

5.7.1.3 Submission of Sequencing Results Previously Obtained as Standard of Care

WES results are available for 16 of the 22 patients who participated on 10250 using tumor biopsies obtained for the study. No results are available for the remaining patients because tissue was not available for various reasons, including technical issues accessing the tumor during the biopsy or poor tumor content. To better understand whether patients with genomic alterations in the HR pathway are more likely to derive clinical benefit from the study treatment and to perform the most complete analysis feasible, we would like to request that sites submit next generation sequencing (NGS) results from NGS assays previously performed as standard of care (i.e. Foundation Medicine, Caris, institutional platform). These reports would be redacted per institutional practice and submitted to the study PI.

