More recently, alterations in ATRX have been implicated in PARPi sensitivity, which is particularly notable given recurrent mutations in ATRX found in LMS (Cancer Genome Atlas Research Network, 2017). ATRX is part of the SWI/SNF2 family of chromatin-remodeling proteins and functions in maintenance of genomic stability through modification of heterochromatin. ATRX has also been shown to localize to sites of DNA damage and associate with the MRE11-RAD50-NBS protein complex which is critical for repairing DSBs and restarting stalled replication forks (Nandakumar et al., 2017). Indeed, in one recent study, ATRX appears necessary for protection of stalled replication forks and when ATRX is lost compensatory PARP activation is observed, suggestive of a mechanism whereby ATRX deficient cancer cells are sensitive to PARPi (Huh et al., 2016). Indeed, very recent literature has suggested that ATRX deficient tumors have markedly enhanced susceptibility to DNA damaging agents including PARPi (Nandakumar et al., 2017; Watson et al., 2015). In one study, patient-derived pediatric glioma cell cultures were exposed to more than 400 chemotherapies and targeted small molecular inhibitors, and synthetic lethality was observed for ATRX mutants treated with the PARP inhibitors olaparib, rucaparib and talazoparib, and these findings were confirmed using CRISPR/Cas9-engineered ATRX knockouts (Fazal-Salom et al., 2017).

Several ongoing clinical trials are evaluating "HR deficiency" gene panels. For example, in an ongoing phase 1 study of niraparib plus carboplatin in patients with HR-deficient advanced solid tumors (NCT03209401), patients are eligible based on biallelic loss or deleterious mutations, as detected by NGS, in the following genes: *ARID1A, ATM, ATRX, MRE11A, NBN (NBS1), PTEN, RAD50/51/51B, BARD1, BLM, BRCA1, BRCA2, BRIP1, FANCA/C/D2/E/F/G/L, PALB2, WRN, CHK2, CHK1, CDKN1A/B/C, CDKN2A, BAP1, FAM175A, SLX4, MLL2, or XRCC.* Weighing the current preclinical and clinical evidence as well as available next generation sequencing data from LMS, we will include *BRCA1, BRCA2, ATM, ATR, ATRX, CHK1, CHK2, RAD51, PALB2, FANCA,* and *NBS1* in our HR panel. A patient will be considered biomarker-positive if a homozygous deletion or deleterious mutation categorized as tier 1-3 is identified in any one of these genes.

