9.4.1.3 Integrated Correlatives

The association between ORR, PFS, and the results of integrated assays evaluating for presence of HR deficiency in the tumor will be evaluated. The two integrated assays are genomics for alterations in HR genes and RAD51 foci formation. Both of these assays report binary results. The rate of response will be compared between binary variables using the Fisher's exact test. The log-rank test will be used to compare PFS between binary variables. Additional results from whole exome sequencing and RNAseq analysis on study samples will be reported in a descriptive fashion.

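### Does requesting standard-of-care NGS reports to supplement study WES leave the HR-gene association analysis open to mis-scoring?

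*Combined protocol and SAP*

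**What the plan says.** All references are to the combined protocol and SAP.

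- **Study assay.** Section 5.6 defines the genomic HR assay as WES with RNAseq. Section 5.7.1.1 fixes the specimen: "Formalin-fixed tissue from the pre-treatment time point will be used for this assay". Section 5.7.1.2 fixes the content: "The assay will specifically evaluate for genomic mutations, copy number changes and loss of heterozygosity in pre-specified HR pathway genes", with 11 genes named.
- **Positivity rule.** Section 2.5.1.1 counts a patient as biomarker-positive "if a homozygous deletion or deleterious mutation categorized as tier 1-3 is identified in any one of these genes".
- **Yield and outside reports.** Section 5.7.1.3 states "WES results are available for 16 of the 22 patients who participated on 10250" and gives reasons for the gaps, "including technical issues accessing the tumor during the biopsy or poor tumor content". It then makes the request: "we would like to request that sites submit next generation sequencing (NGS) results from NGS assays previously performed as standard of care". Commercial and institutional platforms are both acceptable, and on handling it says "These reports would be redacted per institutional practice and submitted to the study PI".
- **Analysis.** Section 9.4.1.3 names two integrated assays, HR-gene genomics and RAD51 foci, and says "Both of these assays report binary results". Response is compared by Fisher's exact test and PFS by the log-rank test. Outside NGS is not mentioned.
- **Status.** Objective 1.2.3 is secondary and calls for a preliminary look at association.

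**The concern.** The positivity rule is asymmetric. One qualifying alteration in any of the 11 genes makes a patient positive, whereas a negative call means something only if all 11 genes, and their deletions, were examined. A single study pipeline can be assumed to meet that condition. An outside panel may not, and Section 5.7.1.3 sets no minimum for gene content, deletion calling, specimen timing or mapping to tiers 1-3. With a two-valued variable and no category for patients who cannot be evaluated, incomplete coverage could slip into the negative group.

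Two further gaps add to the worry. The request is not limited to the patients without WES, so some could have two sources and no rule says which counts. The reports also go to the principal investigator, who under Section 13.1 can see the trial data at all times, and nothing says that calls are made without knowledge of response.

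At stake would be the HR-gene association, and possibly the HR-deficient proportion and the assay-feasibility statement in objective 1.2.3.

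**Working it through.** **How many calls are involved.** From Section 5.7.1.3, 22 − 16 = 6 patients lack study WES, and 6/22 = 27%. This is a ceiling for filling missing calls if WES prevails where both exist. The documents do not say how many of the six have an outside report. Study-WES yield is 16/22 = 73%, exact 95% CI 50% to 89%.

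**The primary rule, for reference.** Section 9.1.3 requires 5 or more responses in 22. The exact binomial calculation gives P(X ≥ 5 | 10%) = 0.0621 and P(X ≥ 5 | 35%) = 0.9284, which agrees with the stated 6% and 93%. Biomarker status does not enter this rule.

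**How far six labels can move the association.** The documents give no biomarker results, so every split here is assumed. All p-values are two-sided Fisher.

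| Assumed data | Responders, HR+ vs HR− | p |
|---|---|---|
| WES only | 4/8 vs 1/8 | 0.28 |
| plus six non-responders, all called negative | 4/8 vs 1/14 | 0.039 |
| plus six, three called positive | 4/11 vs 1/11 | 0.31 |
| plus six, all called positive | 4/14 vs 1/8 | 0.61 |
| WES only, another split | 5/8 vs 0/8 | 0.026 |
| plus six non-responders, all called negative | 5/8 vs 0/14 | 0.0021 |
| plus six, all called positive | 5/14 vs 0/8 | 0.115 |

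The arithmetic sensitivity is therefore real. It is also conditional. Keep the 4-versus-1 responder split, let all six be non-responders with reports, and vary the number HR+ among the 16:

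| HR+ of 16 | Range of p over 0 to 6 positive labels |
|---|---|
| 5 | 0.003 to 0.31 |
| 6 | 0.009 to 0.32 |
| 7 | 0.021 to 0.36 |
| 8 | 0.039 to 0.61 |
| 9 | 0.116 to 1.0 |
| 10 | 0.135 to 1.0 |
| 11 | 0.31 to 1.0 |

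From 9 of 16 (56%) upward, the labels no longer cross 0.05 under that split. Section 2.4 cites a sequencing series of 49 leiomyosarcoma patients with BRCA2 alterations in 53%, before the other ten genes are counted. That points toward the upper rows, with the caution that the series includes non-uterine tumors and may define alterations more broadly.

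**Does the text produce the mis-scoring?** Reading the sections together:

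1. Section 2.5.1.1 defines when a patient is positive. It does not say that a gene nobody tested makes a patient negative.
2. In Section 9.4.1.3 the two-valued results belong to the two integrated assays, and Section 5.6 identifies the genomic one as study WES/RNAseq. Pooling with outside panels is not stated.
3. Section 5.7.1.3 asks for outside reports in order to study association with benefit. It does not send them into the HR-deficient proportion or the feasibility figure, and it reports study-WES yield separately. A fall from 8/16 (50%) to 8/22 (36%), again with assumed counts, would need a use of the reports that the plan does not describe.
4. Loss of heterozygosity is part of what study WES examines but not of the positivity rule, so a panel without it can still give the same binary call.

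**The case for a change.** The strongest case for a change is that calling an analysis preliminary does not excuse an undefined variable. Section 9.4.1.3 names formal tests, six labels are 27% of the data, and rules written after the results are seen cannot be shown to be independent of outcome. Errors can also run the other way: an assumed true split of 5/12 versus 0/10 gives p = 0.040, and one responder's alteration missed by a panel turns it into 4/11 versus 1/11, p = 0.31.

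Part of this stands. The handling rules are not written down, and outside reports carry no specimen, germline or tier requirement, so they are not guaranteed to be equivalent to study WES. What does not stand is the step from silence to harm. No alpha is set for this comparison and nothing is decided by crossing 0.05.

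Prescribed rules would not be free of bias either:

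- **Treating an incomplete report with no alteration as not evaluable, while accepting one with an alteration,** lets incomplete panels add only HR+ patients. If the six non-responders in the first example split three and three, the comparison becomes 4/11 versus 1/8, a difference of 36.4% − 12.5% = 23.9 points. With all six kept it is 4/11 versus 1/11, or 36.4% − 9.1% = 27.3 points.
- **Making the 16 WES patients the reference set** can lose a true signal. If the six in the 5/12 versus 0/10 example are three HR+ (one of them a responder) and three HR−, WES alone gives 4/9 versus 0/7, p = 0.088. The choice would also be post hoc, since the WES results already exist.
- **Making calls before linkage to response** is hard to guarantee in an open-label trial when the person receiving the reports already has the data.

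**Conclusion.** No change to the plan is needed. The gap is real but small: an unwritten handling rule for an optional supplement to a preliminary secondary analysis. A competent analyst would identify each call by source, use study WES where both exist, decide from coverage of the 11 genes and their deletions (not from the result) whether an outside report can be scored, and show the association with and without the outside reports. Nothing in the documents prevents that, and nothing in them directs that untested genes be scored as negative.

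The reach is at most 6 of 22 calls, assuming WES prevails and all six patients have a report, which the documents do not establish. The p-value swings shown, such as 0.039 to 0.61, rest wholly on assumed splits and trigger no decision. The HR-deficient proportion and feasibility figures are not stated uses of these reports, and the primary rule of 5 responses in 22 is untouched.
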